NCT04805515

Impact of Nicotine Messaging on Nicotine Beliefs and Tobacco Use Behavior

Document date: December 18, 2020

Contents

Study Protocol.....	2
Study Measures	3
Statistical Analysis Plan	4
References	6

Study Protocol

The current study tests the impact of multiple exposures to a brief nicotine corrective messaging intervention on beliefs about nicotine and on intention and use of tobacco and nicotine products in a 12-week population-based study of 794 adult smokers and non-smokers who are registered Amerispeak national consumer market research panel members. Data were collected by National Opinion Research Center (NORC) at the University of Chicago and sent de-identified to the PI and study team. A parallel lab-based study will be conducted in adult smokers followed for 4 weeks (NCT05108649) who also receive normal nicotine content or reduced nicotine content cigarettes and are explicitly told which product they have been given (i.e., unblinded).

For the population-based study, AmeriSpeak panel members received a standard email invitation describing the study. NORC obtains and documents participants' informed consent at the time of registration in the Amerispeak panel. Potential participants are identified by randomly selecting households within the panel with an adult within the study age range, and targeting study invitations based on recent study participation, and other demographic characteristics as needed to ensure a representative sample. This email invitation introduced study procedures and eligibility criteria, and directed interested panel members to the eligibility screener with items to confirm eligibility. Procedures ensured that potential participants are adults ages 18 and older through two steps: 1) targeting study invitations only to those panel members whose age was within this range; and 2) re-assessing age at eligibility screening and excluding those who provide inconsistent information. Panel members who were confirmed to meet study eligibility criteria proceeded to the online experiment. AmeriSpeak panel members who did not meet study eligibility criteria were redirected to a concluding thank-you screen.

The Nicotine Corrective Messaging (NCM) intervention condition was based on messages tested in our team's pilot study.¹ It included the following six original messages and two new messages addressing nicotine in cigarette and e-cigarette products that were adapted from several evidence-based sources to be more accessible to a lay audience. The sources consisted of FDA's 2017 comprehensive plan for tobacco and nicotine regulation,² FDA's 2013 modifications to labeling of NRT products for over-the-counter human use,³ the 2014 U.S. Surgeon General's Report on the Health Consequences of Smoking,⁴ reports on carcinogens from the International Agency for Research on Cancer,⁵⁻⁷ and the NASEM report on the "Public Health Consequences of E-cigarettes.⁸ Participants in the NCM condition were exposed to all eight messages in the same order at each exposure.

Upon study enrollment, participants completed baseline questions about tobacco use behavior, nicotine beliefs, and other measures (see Study Measures). After completing the baseline survey, participants were randomly assigned in equal numbers to the Nicotine Corrective Messaging (NCM) intervention condition or the delayed message control condition. Participants in the NCM condition then received their first exposure to the study messages. Participants viewed each image in the NCM condition for at least 5 seconds, and we assessed self-reported visual attention using a heatmap task. We allowed for three weeks to maximize the collection of Wave 1 (Weeks 1-3) and Wave 4 (Weeks 10-12) data and two weeks for Wave 2 (Weeks 4-5) and Wave 3 (Weeks 7-8). In the Wave 2 survey (Weeks 4-5), all participants completed measures of nicotine beliefs and intentions/use of nicotine and tobacco products; this provided the first post-exposure measures of the key outcomes. Participants in the NCM condition then received their second exposure to study messages and completed the heatmap task. Only participants in the NCM condition received the Wave 3 survey (Weeks 7-8), which comprised the third exposure to study messages and the heatmap task. The Wave 4 survey (Weeks 10-12) included the final survey assessment of key measures, followed by exposure to NCM messages and heatmap task for all participants.

Study Measures

	Aim 1: Population study	Aim 2: Lab study
Intervention/Exposure		
Nicotine messaging vs. control	Wave 1	Week 1
Normal nicotine vs. RNC cigarette		Week 1
Heatmapping	Waves 1-4	
Perceived message effectiveness	Wave 4	Week 5
Message credibility	Wave 4	Week 5
Eye-tracking		Weeks 1-4
Biomarkers		Weeks 0, 5
Outcomes		
Nicotine beliefs	Waves 1, 2, 4	Weeks 0, 2, 5
Intention to use nicotine/tobacco products	Waves 1, 2, 4	Weeks 0, 2, 5
Nicotine/tobacco use and behavior	Waves 1, 2, 4	Weeks 0, 2, 5
Subjective rating of study cigarette		Weeks 1-5
Manipulation check	Waves 1, 2, 4	Weeks 0, 2, 5
Moderators		
Sociodemographics	Wave 1	Week 0
Literacy	Wave 1	Week 0
Cancer risk beliefs	Wave 1	Week 0
Cancer risk behaviors	Wave 1	Week 0
Fagerstrom test for nicotine dependence	Wave 1	Week 0
Other key constructs		
Attitudes about nicotine	Waves 1, 2, 4	Weeks 0, 2, 5
Nicotine-related norms	Waves 1, 2, 4	Weeks 0, 2, 5
Behavioral control	Waves 1, 2, 4	Weeks 0, 2, 5
Stages of change	Wave 1, 4	Week 0, 5
Policy support	Wave 4	Week 5

Statistical Analysis Plan

Sample Size. Power for Aim 1 was calculated for 715 adults with 70% retention at 12-weeks follow-up. Our pilot data provide estimates of the magnitude of the effect of the Nicotine Corrective Messaging (NCM) intervention on the primary outcome of nicotine beliefs, including four continuous scales on nicotine false beliefs, NRT false beliefs, e-cigarette false beliefs, and reduced nicotine content (RNC) cigarette false beliefs.¹ With an expected final sample size of 500 and ignoring repeated measures, we will have 80% power to detect differences of <1 unit between the intervention and control group means for the nicotine, NRT, and e-cigarette false belief scales and a 1.64 difference in the group means for the RNC cigarette false beliefs scale. These equate to small-to-medium effect sizes (Cohen's *d* ranging from 0.25 to 0.27), which are smaller than the effects observed for nicotine and NRT false beliefs outcomes in the pilot study.¹

Data Preparation. Prior to performing all analyses, standard data screening/cleaning procedures will be applied. These procedures will (1) screen the data for data recording errors, (2) check for outliers, (3) assess the extent and pattern of missing data, and (4) check that appropriate assumptions of normality are met whenever necessary. In all analyses, the assumptions underlying the application of all the statistical methods that are used will be examined, principally using standardized residuals, influence diagnostics, and graphical displays. Where needed, appropriate transformations will be applied to ensure that data meet model assumptions. Descriptive analyses will characterize participants overall and by study condition. Bivariate tests will assess for differences in participant characteristics by intervention condition (NCM vs. control) and examine if any baseline variables that are imbalanced between study groups are associated with primary and secondary outcomes (*p* < .10). Any such variables will be accounted for in analyses as covariates.

Analytic Approach.

Aim 1: Test the impact of nicotine corrective messaging (NCM) on nicotine beliefs and the subsequent impact on intention and use of tobacco and nicotine products in a national sample of 715 adult smokers and non-smokers followed for 12 weeks.

Hypothesis 1a: Adults in the NCM condition will report fewer false beliefs about nicotine, NRT, e-cigarettes and RNC cigarettes and lower intentions to use tobacco and nicotine products at follow-up compared to those in the control condition.

Hypothesis 1b: Current smoking will moderate the effect of NCM on false beliefs of nicotine, NRT, e-cigarettes, and RNC cigarettes and intended use of tobacco and nicotine products at follow-up. The effect of NCM on these outcomes will be attenuated in adult smokers compared to non-smokers.

Analyses for Aims 1 and 2 employ common measures and a common analytic framework to test the impact of nicotine education on nicotine beliefs and behavior. Primary analyses will use an intention-to-treat approach. We will conduct sensitivity analyses with different assumptions for the missing data mechanism including analyzing complete data only⁹ and last observation carried forward. Outcomes for Aim 1 focus on continuous measures (*primary outcome*: nicotine beliefs; *secondary outcomes*: frequency of nicotine/tobacco use), with the primary hypotheses (**Hypotheses 1a**) focused on the effect of the intervention on these outcomes. Preliminary analyses will examine differences in these outcomes across study conditions at the first post-exposure time point (Wave 2) and at the final timepoint (Wave 4) controlling for covariates that are differentially distributed between study groups. In Aim 1, we will also use multiple logistic regression models to examine effects of the NCM intervention on the proportion of participants reporting specific nicotine beliefs (i.e., "nicotine is a cause of cancer"), intentions to use cigarettes, e-cigarettes, NRT, and low nicotine cigarettes in the next 12 months, and

tobacco/nicotine use (e.g., any new use/trial, any past 30-day use, product-specific past 30-day use).

For **Hypothesis 1b**, we will evaluate whether current smoking moderates the effect of NCM on our primary and secondary outcomes by incorporating an interaction between study condition (NCM/control) and current smoking status (smoker/non-smoker) through the following steps: 1) bivariate analyses, to determine if outcomes vary by these variables; 2) testing whether current cigarette smoking moderates ($p < .05$) experimental effects in the models above by the addition of a study condition-by-smoking status interaction term into the model; 3) if no evidence of moderation exists, including cigarette smoking as a covariate.

Exploratory analyses will focus on three areas: 1) potential moderators of the relationship between intervention condition and the study outcomes; 2) nicotine beliefs as a potential mediator of the relationship between intervention condition and constructs identified in the Theory of Planned Behavior (i.e., nicotine-related attitudes, norms, behavioral control, and nicotine/tobacco intentions and use); and 3) the relationship between visual attention to nicotine education messages and nicotine beliefs in the participants exposed to the NCM intervention.

For the first area (*moderation*), we will conduct exploratory analyses using the same steps described for Hypothesis 1b to determine whether there are potential moderators of the relationship between the intervention(s) and outcomes, specifically age, gender, literacy, baseline cancer beliefs and cancer risk behaviors.

For the second area (*mediation*), we will draw from traditional mediation frameworks and use robust methods to explore the relationships outlined in our theoretical framework, specifically whether changes in nicotine beliefs post-exposure (Wave 2) influence nicotine-related attitudes, norms, behavioral control, intention, and behavior at the final assessment (Wave 4). We will examine whether nicotine beliefs at Wave 2 are associated with these outcomes using bivariate statistics and regression-based analysis accounting for any covariates as described above. Where these preliminary steps indicate potential correlation between nicotine beliefs and study outcomes ($p < .05$), we will test for mediation by estimating the indirect effects of nicotine beliefs on follow-up outcomes via the intervention condition using a bias-corrected bootstrapping method with 1,000 resamples. This approach estimates indirect (i.e., mediation) effects and produces bias-corrected asymmetric 95% CIs correcting for non-normality of the distribution of indirect effects and providing higher power and better control over the Type I error rate versus traditional approaches to test mediation. Asymmetric 95% confidence intervals around indirect effect estimates for nicotine beliefs that do not include zero will be interpreted to indicate significant mediation.

For the third area (*visual attention*), we will use data from the Wave 1 heatmapping task among participants in the NCM condition to identify regions of interest (ROIs) on each of the nicotine education messages and code these as ROIs across all Waves. We will explore whether attention to (i.e., clicking on) the ROIs is correlated with scores on the nicotine beliefs scales (i.e., nicotine, NRT, e-cigarette, RNC cigarette beliefs) at the same assessment (Wave 4). Given the content of messages in the nicotine education condition, we will be able to assess whether attention to specific ROIs is correlated with specific beliefs (i.e., whether clicking on a specific ROI within the “Nicotine does not cause cancer” is correlated with response to the nicotine belief item regarding nicotine causing cancer). We will also be able to explore the prospective relationship between visual attention to the nicotine education messages (e.g., duration spent viewing messages, attention to ROIs) and nicotine beliefs and whether there are differences in visual attention in the NCM intervention condition over the four waves of data collection. These data will inform potential refinements to nicotine education messages for future studies.

Missing data: The most effective approach to eliminating biases and inefficiency caused by missing data is to collect complete data. In both aims of our study, we will use several tools available to maintain contact and verify that forms are complete. Use of computerized survey platforms in this study will provide additional mechanisms to improve completeness of survey responses, but even so, some participants may refuse to answer certain questions. We anticipate that one cause of missing data will be item non-response on self-report questionnaires; another will be missing assessments. When practical, missing items will be imputed using conditional means, estimated with an iterated version of Buck's method.¹⁰ Another cause of missing data is attrition, and we will pursue a range of model-based analyses that account for dropouts assuming data are missing at random (MAR), including multiple imputation methods (MI).^{11,12} We will also conduct sensitivity analyses with different assumptions for the missing data mechanism including analyzing complete data only⁹ (missing completely at random, MCAR) and last observation carried forward, in which subjects without self-report follow-up data will be considered to have no change.

References

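### The past 30-day use models name no wave; at Wave 2 most possible look-backs would reach before randomisation, so Wave 4 should be named for the comparison between arms

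*Combined protocol and SAP*

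**What the plan says.** **Timing.** The Study Protocol section states "After completing the baseline survey, participants were randomly assigned in equal numbers", so randomisation falls on the day of the Wave 1 survey. It allows "three weeks to maximize the collection of Wave 1 (Weeks 1-3) and Wave 4 (Weeks 10-12) data and two weeks for Wave 2". On Wave 2 it adds: "In the Wave 2 survey (Weeks 4-5), all participants completed measures of nicotine beliefs and intentions/use of nicotine and tobacco products". It presents this survey as the earliest reading of the main outcomes after exposure. The Study Measures table schedules use at Waves 1, 2 and 4.

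**Analysis.** The Analytic Approach lists beliefs as primary and "frequency of nicotine/tobacco use" as secondary. It describes as preliminary a comparison of these continuous outcomes "at the first post-exposure time point (Wave 2) and at the final timepoint (Wave 4"). The next sentence adds logistic models for specific beliefs, intentions and "tobacco/nicotine use (e.g., any new use/trial, any past 30-day use, product-specific past 30-day use"). That sentence names no wave.

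**Covariates.** Under Hypothesis 1b, smoking status enters "by the addition of a study condition-by-smoking status interaction term into the model" or, failing that, as a main effect: "if no evidence of moderation exists, including cigarette smoking as a covariate". Under Data Preparation, any other baseline variable, including the Wave 1 value of the same use item, enters only if it is imbalanced between arms and associated with outcome.

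**The concern.** A 30-day recall item measures the effect of an intervention cleanly only when all 30 days follow randomisation. Wave 2 opens the day after the Wave 1 field period closes, so a participant could be asked about the past 30 days very soon after being randomised. Use before randomisation would then be counted as outcome.

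This matters most for stopping. A person who used before randomisation and then stopped is still recorded as a past 30-day user while any of the earlier use lies inside the window. A null Wave 2 result could be read as no effect on behaviour when the item could hardly have shown one. With no wave named, the choice between Wave 2 and Wave 4 could also be made after the results are seen.

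**Working it through.** **The plan's own figure.** The documents give no interval from randomisation to Wave 2 and no power for use. The only design calculation concerns the belief scales at 12 weeks. 715 × 0.70 = 500.5, which reproduces the stated 500. With 250 per arm and two-sided alpha 0.05 (assumed, because the power statement gives none), power at d = 0.25 is 79.8%, which reproduces 80%. This calculation does not cover the use outcomes.

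**Inputs (Study Protocol), with week w = days 7(w-1)+1 to 7w.**
- Wave 1 and randomisation: Weeks 1-3 = days 1-21
- Wave 2: Weeks 4-5 = days 22-35
- Third exposure (Wave 3, messaging arm only): Weeks 7-8 = days 43-56
- Wave 4: Weeks 10-12 = days 64-84

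**Definitions.** Gap g = survey day minus randomisation day. The look-back is the survey day and the 29 days before it. It lies wholly after the randomisation day when g ≥ 30. Otherwise it holds 30 - g days that are not after randomisation.

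**Wave 2, calendar windows.**
- Smallest gap 22 - 21 = 1; largest 35 - 1 = 34.
- Day pairs: 21 × 14 = 294.
- Clean pairs (g ≥ 30): randomisation on day 1, 2, 3, 4 or 5 leaves 5, 4, 3, 2 or 1 eligible Wave 2 days, a total of 15, or 15/294 = 5.1%.
- Pairs with overlap: 294 - 15 = 279, or 94.9%.

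**Wave 2, each participant's own clock (alternative reading).** With Wave 1 on day 1 and Wave 2 on days 22-35, g = 21-34. The gap is under 30 on 9 of 14 days (64%).

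**Stopping.** Last use k days after randomisation lies outside the window only if g - k ≥ 30. On either clock the largest gap is 34, so k can be at most 34 - 30 = 4. Last use at k ≥ 5, provided it precedes the Wave 2 survey, always counts as past 30-day use.

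**Wave 4.**
- Calendar gap: 64 - 21 = 43 to 84 - 1 = 83. Own clock: 63-83. All exceed 30, so there is no overlap.
- Limit on k, calendar windows: 43 - 30 = 13 days at the shortest gap, 83 - 30 = 53 at the longest.
- The third exposure precedes Wave 4 by 64 - 56 = 8 to 84 - 43 = 41 days, so stopping after it can still be hidden.

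**Frequency of use, only if it is a 30-day count (assumption).** An immediate constant change in daily use would show at a fraction 1 - (mean overlap days)/30.
- Calendar windows, uniform response assumed: mean gap 17.5, so the mean of 30 - g is 12.5. Pairs with g above 30 contribute no overlap, which adds (4×1 + 3×2 + 2×3 + 1×4)/294 = 20/294 = 0.07. Mean overlap is 12.6 days; fraction 1 - 12.6/30 = 58%.
- Own clock, uniform response assumed: (9 + 8 + ... + 1)/14 = 45/14 = 3.2 days; fraction 1 - 3.2/30 = 89%.

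**Share of participants.** Day pairs are not participants. Under other assumed response patterns on calendar windows, the share with a gap under 30 days runs from 10.9% (Wave 1 returns concentrated on the first days and Wave 2 returns on the last) to 100% (all Wave 1 returns in Week 3). The documents do not fix it.

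**The case against.** The strongest reply is that the plan never commits the 30-day models to Wave 2. The sentence naming Waves 2 and 4 concerns the continuous outcomes and is labelled preliminary. Other cues point to Wave 4: Aim 1 follows participants for 12 weeks, power is set at 12 weeks, and the mediation analysis takes behaviour at the final assessment. This stands, and it makes the point conditional. It does not remove the gap, because no section sets a Wave 4-only rule, a minimum interval or a shorter Wave 2 look-back, and the protocol counts use among the Wave 2 measures.

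Further points also stand in part:
- The questionnaire is not reproduced and may define the look-back differently. The SAP itself, however, names the outcome as past 30-day use.
- The missing wave affects the belief and intention items in the same sentence too. They do not share the 30-day recall problem.
- Both arms share the overlap, so type I error is not inflated. Balance does not undo the dilution.
- Wave 4 is not a full cure. Thirty-day prevalence hides recent stopping at any survey; Wave 4 removes only the pre-randomisation part.
- Adjusting for the Wave 1 measure does not address the overlap. It is a separate gain in precision.

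**Conclusion.** The point holds as a minor one. The models for past 30-day use need a named wave, and the plan's own field windows make Wave 4 the only post-randomisation assessment of use whose 30-day look-back never reaches before randomisation. That result holds on both readings of the calendar. If the models are run at Wave 2, the consequence is dilution of any stopping effect, and of change in either direction for frequency if that is a 30-day count. New use after exposure is still captured. Beliefs and the mediation analysis are unaffected.

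A reader might infer more than the documents support:
- That the plan makes Wave 2 30-day use a formal test. It does not say so.
- That about 95% of participants are affected. That figure counts calendar day pairs; response timing is not given.
- That the comparison is biased in favour of one arm. The overlap is common to both.
- That a bias or power loss can be stated. The documents give no use rates and no expected effect on use, and they do not give the questionnaire's look-back.

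**What to change.** In the Analytic Approach, add text such as: *Use outcomes with a 30-day look-back, including frequency of use if it is a 30-day count, will be compared between arms at Wave 4. Wave 2 values will be reported as supportive for all randomised participants, with days since randomisation by arm; the Wave 2 window can include days before randomisation.*

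Separately, for precision, adjust these models for the same use measure at Wave 1 whether or not it is imbalanced, except where a product is too rarely used for the model to be fitted. This replaces the Data Preparation rule for these outcomes only.

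The cost is small. Wave 1 and Wave 4 use are already scheduled, so no new data are needed, and loss to follow-up by 12 weeks is already assumed in the 70% retention. Wave 2 results are kept but carry less weight. Because the Study Protocol section describes data collection in the past tense, the change should be dated and justified, with a statement of whether results by arm had been seen.

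### The Wave 1 belief score is not a prespecified covariate; adjusting only for baseline variables found imbalanced gives up precision and makes the primary comparison conservative

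*Combined protocol and SAP*

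**What the plan says.** In the Study Protocol section, on enrolment "participants completed baseline questions about tobacco use behavior, nicotine beliefs, and other measures". Allocation comes next: "After completing the baseline survey, participants were randomly assigned in equal numbers". The Study Measures table lists nicotine beliefs at Waves 1, 2 and 4. A pre-randomisation value of each primary scale is therefore available for everyone randomised who answered it.

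The covariate rule is in the SAP under Data Preparation. Arms are compared on baseline characteristics, and the analysts then "examine if any baseline variables that are imbalanced between study groups are associated with primary and secondary outcomes", with p < .10 given in brackets. It continues: "Any such variables will be accounted for in analyses as covariates".

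Under Analytic Approach, the continuous outcomes are compared between arms at Wave 2 and Wave 4, "controlling for covariates that are differentially distributed between study groups". The SAP calls this comparison preliminary and writes out no other model for Hypothesis 1a.

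The one other covariate named is smoking status. Under Hypothesis 1b it is tested as an interaction and, "if no evidence of moderation exists, including cigarette smoking as a covariate".

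**The concern.** In a randomised trial the reason to adjust for a baseline variable is that it predicts the outcome, not that it happens to differ between arms. The Wave 1 score of the same scale is usually a strong predictor of the follow-up score. A rule that admits it only after a chance imbalance discards it in most trials.

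Three consequences follow:

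- **Precision.** Outcome variance that Wave 1 could explain stays in the error term. The Hypothesis 1b interaction is added to the same models, so it inherits that variance.
- **Conservatism.** When baseline is balanced, the arm difference varies less than the unadjusted standard error assumes, so the test rejects too rarely under the null.
- **Data dependence.** The covariates behind the Hypothesis 1a estimate are fixed only after baseline data, and through the association screen outcome data, have been seen.

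The rule itself is also loosely stated. Data Preparation requires imbalance and association, while Analytic Approach mentions imbalance alone. It is unclear whether p < .10 governs imbalance, association or both.

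**Working it through.** **Inputs from the documents.** 715 enrolled and 70% retention (Sample Size): 715 × 0.70 = 500.5, matching the stated 500, or 250 per arm. Power is 80% and d is 0.25 to 0.27 (same section). The Study Protocol gives 794 participants: 794 × 0.70 = 555.8, about 556.

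**Assumptions.** Two-sided alpha of .05, which is not stated. The correlation r between Wave 1 and follow-up scores is not given; the range 0.3 to 0.7 is used. Outcomes are taken as normal.

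**1. The plan's own figure.** Detectable d at 80% power, unadjusted:

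(1.960 + 0.842) × √(2/250) = 2.802 × 0.0894 = 0.251

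Power at d = 0.25 is 79.8%. The lower end of the stated range is reproduced. At the upper end, d = 0.27, power with 500 would be 85.5%; that end is not used below.

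**2. Always adjusting for Wave 1.** ANCOVA multiplies the outcome SD by √(1 − r²), so the detectable d becomes 0.2506 × √(1 − r²). Total N is for 80% power at d = 0.25, against 504 unadjusted.

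| r | Detectable d | Power at d = 0.25, N = 500 | Total N |
|---|---|---|---|
| 0.3 | 0.239 | 83.4% | 458 |
| 0.4 | 0.230 | 86.2% | 422 |
| 0.5 | 0.217 | 89.8% | 378 |
| 0.6 | 0.200 | 93.7% | 322 |
| 0.7 | 0.179 | 97.5% | 258 |

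**3. The plan's rule.** Simulation, 40,000 trials per cell, 250 per arm. Wave 1 enters only if its imbalance p is below the cut-off and its association p is below .10. Monte Carlo standard error is about 0.2 points for power and 0.1 for type I error.

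| r | Power, unadjusted | Power, rule (.10) | Power, always adjusted | Type I, rule (.10) | Power, rule (.05) | Type I, rule (.05) |
|---|---|---|---|---|---|---|
| 0.3 | 80.0% | 80.7% | 83.6% | 4.7% | 80.2% | 4.7% |
| 0.4 | 79.7% | 80.9% | 86.2% | 4.4% | 80.2% | 4.5% |
| 0.5 | 79.5% | 81.5% | 89.5% | 4.0% | 80.7% | 4.3% |
| 0.6 | 79.7% | 82.5% | 93.7% | 3.5% | 81.3% | 3.9% |
| 0.7 | 79.8% | 83.5% | 97.5% | 3.1% | 81.7% | 3.6% |

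Type I error was 4.9% to 5.1% for both the always-unadjusted and the always-adjusted test. Wave 1 was selected in about 10% of trials at the .10 cut-off and 5% at .05.

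A separate run omitting the association screen, which is nearly always passed at these r and N, agrees. At cut-off .10 and r = 0.3, 0.5 and 0.7, power under the rule was 80.9%, 81.6% and 83.7%, and type I error 4.7%, 4.0% and 3.1%.

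**4. Why the rule is conservative.** If imbalance is tested at .10, a trial judged balanced has a standardised baseline difference within ±1.645. Truncation reduces its variance to 1 − 2 × 1.645 × 0.1031/0.90 = 0.623. The standardised outcome difference then has variance 1 − 0.377r², while the unadjusted test assumes 1.

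At r = 0.7 this is 1 − 0.377 × 0.49 = 0.815, an SD of 0.903. Rejection probability is P(|Z| > 1.96/0.903 = 2.17) = 3.0%. Weighting balanced trials (unadjusted) and imbalanced trials (ANCOVA, 5%) gives 0.9 × 3.0% + 0.1 × 5% = 3.2%, close to the simulated 3.1%.

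**5. At 556 analysed, cut-off .10.** Unadjusted power is 83.7%. Rule against always adjusting: 84.2% and 86.8% (r = 0.3), 85.6% and 92.6% (0.5), 87.2% and 98.5% (0.7).

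**The case against.** The strongest reply is that the comparison is labelled preliminary. The sample size statement sets repeated measures aside, and the Missing data section promises model-based analyses under MAR, including multiple imputation. A longitudinal model using Wave 1 would fit that text, so the real gap may be an unspecified primary model. This stands to the extent that the power and type I figures describe the analysis as written and not every analysis the text would allow. It does not remove the imbalance rule: none of those sentences names the Wave 1 score or defines the Hypothesis 1a model.

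A second reply is that nothing invalid results and the plan meets its own power target. That is true; the point concerns efficiency and prespecification.

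Third, the gain depends on an assumed r. At r = 0.3 it is about 3 points of power at the .10 cut-off, and the 14-point gain needs r = 0.7. The documents favour neither end.

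Fourth, the simulation screens one covariate. Other Wave 1 variables correlated with beliefs might enter, and smoking status is modelled under Hypothesis 1b on either branch, which could recover some precision. But the plan does not say that the Hypothesis 1a estimate comes from that model, and smoking status is not the belief score.

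Last, much of the protocol is in the past tense. If outcome data have been seen, changing the covariates is a post-data change and must be declared as one.

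**Conclusion.** The concern holds. The Wave 1 score of each belief scale is collected before randomisation, is not a prespecified covariate, and under the written rule is used only after a chance imbalance.

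At N = 500 and d = 0.25, the power forgone relative to always adjusting is about 3 points at r = 0.3, 8 at r = 0.5 and 14 at r = 0.7, with imbalance judged at .10. With the .05 cut-off the loss is slightly larger (3.4, 8.8 and 15.8 points) and the conservatism slightly weaker at the higher correlations.

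These sizes rest on the assumed r, two-sided alpha of .05, normal outcomes, a single screened covariate, and the Wave 2 and Wave 4 comparison being the Hypothesis 1a analysis. The omission itself rests on none of these. It should be fixed, but it does not threaten the validity of the trial.

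**What to change.** - Drop the imbalance and association screen for the treatment comparison, and keep baseline comparisons between arms descriptive.
- For each continuous belief scale, and each secondary frequency outcome with a Wave 1 value, prespecify ANCOVA or a Wave 2/Wave 4 repeated-measures model. Its covariates are the Wave 1 value of that outcome and Wave 1 smoking status, whatever the balance.
- State that the Hypothesis 1a effect is reported from this model regardless of the Hypothesis 1b interaction test.
- For the binary outcomes ("any new use/trial, any past 30-day use, product-specific past 30-day use", the belief items and the intentions), include the Wave 1 item where one exists, and say that the odds ratio is conditional on the covariates. The exception is new use or trial. The plan does not define it, but it reads as relative to baseline use, so define it and leave that item out of its model.

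The gain was computed only for a continuous outcome; for the secondary and binary outcomes the change is for consistency.

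The cost is SAP wording. The covariates are already collected at Wave 1, and sample size and procedures do not change. If outcome data have already been examined, date and justify the change, and report the adjusted model as a labelled sensitivity analysis.
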